3.3 RATIONALE FOR STUDY DESIGN

The main study is a Phase IIIb, prospective, multicenter, open-label singe-arm study to assess the effectiveness and safety of ocrelizumab in patients in the early stage of RRMS.

Ocrelizumab—F. Hoffmann-La Roche Ltd 38/Protocol MA30143, Version 10.0 As the efficacy and safety of ocrelizumab has already been demonstrated in pivotal double-blind, randomized controlled trials as described in Section 1.2, a single arm approach for this study, where the goal is to characterize the clinical profile of the drug in early patients, is considered to be appropriate. As the effect of existing standard of care treatments on the clinical course of early RRMS is already well established in the literature (Noyes and Weinstock-Guttman 2013; Rudick et al.2010), no direct comparators are required for this study. The main analyses will be in the form of descriptive statistics examining change from baseline to endpoint across the outcome parameters for the entire study sample, and for sub-groups of interest. A study duration of 4 years is considered to be sufficient to show a reliable and relevant effect of ocrelizumab on disability progression (EMA/CHMP/771815/2011, Rev. 2, 2015). Given the potentially long-term use of ocrelizumab in MS, this study of 4 years duration will provide additional safety data in a population with early stage of RRMS to be contextualized with the population studied in the pivotal phase III trials.

The effectiveness of ocrelizumab will be evaluated based on various clinical outcomes related to disease progression over 4 years.

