6. STATISTICAL CONSIDERATIONS AND ANALYSIS PLAN

The analysis of this open label, single arm study will be descriptive and primarily based on descriptive statistical methods. Unless otherwise specified, statistical tests will be exploratory in nature. Corresponding 95% CIs will be presented as appropriate. No correction for multiple testing will be applied.

Full details of all statistical aspects and planned statistical analyses will be specified in a separate Statistical Analysis Plan (SAP), which will be finalized prior to the locking of the study database and may include further exploratory analyses not explicitly described in this section, as well as analyses of data from the study phase beyond the main 192week study period, e.g., safety follow-up information.

Analysis populations

The primary effectiveness and safety analyses will be performed using the intent-to-treat (ITT) population. The per-protocol (PP) population will be used for supportive effectiveness analyses of selected effectiveness endpoints in order to evaluate the influence of major protocol violators on key effectiveness endpoints.

ITT Population

All enrolled patients who received any dose of ocrelizumab will be included in the ITT population. Patients who prematurely withdrew from the study for any reason will still be included in the ITT population.

PP Population

The PP population will include all ITT patients without protocol deviations deemed to affect the assessment of effectiveness. The list of criteria leading to exclusion from the PP population will be finalized prior to database closure and documented in the SAP.

Ocrelizumab—F. Hoffmann-La Roche Ltd

85/Protocol MA30143, Version 10.0

Safety Population

The safety population will include all enrolled patients who received any dose or part of a dose of ocrelizumab.

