6.1 DETERMINATION OF SAMPLE SIZE

The main study is a single-arm effectiveness and safety study. There is no formal statistical hypothesis and all analyses will be descriptive. The results for the key endpoints will be presented in a descriptive analysis including the corresponding 95% the confidence intervals.

Sample size considerations for the main study are based on pooled data from two ocrelizumab phase III trials in RRMS (OPERA I and II). Based on extrapolations from these studies, we can conservatively expect 15% of patients (or less) to have a CDP event and approximately the same number of patients to be prematurely withdrawn and censored before week 192.

In this case, for 1,100 patients, the precision (half-width of the 95% confidence interval) of the estimated CDP rate by study end is expected to be approximately 1.8%, i.e., the 95% confidence interval of (13.2%, 16.8%).

In OPERA the EDSS improvement at 2 years had a standard deviation of 0.74, based on 240 patients from the ocrelizumab group, who were previously treatment-naïve with disease duration \leq 3 years and EDSS \leq 3.5. The standard deviation was rather stable over time and is assumed to remain stable after four years of treatment. A sample size of 1,100 patients is expected to provide a precision for the estimate of the EDSS change from baseline of about 0.037, assuming a standard deviation of 0.75. Assuming no EDSS change from baseline, the 95% confidence interval is expected to be (-0.074, 0.074).

The main study was initially planned to enroll at least 600 patients. Approximately 550 additional patients were to be enrolled in the shorter infusion sub-study. They would also be enrolled in the main study (see Appendix 10 for more details). Therefore, the main study would enroll a total of at least 1,100 patients. A total of 1,225 patients (678 in the main study and 547 in the shorter infusion substudy) were enrolled in the study.

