6.4 EFFECTIVENESS ANALYSES

6.4.1 Effectiveness Endpoints

Effectiveness of ocrelizumab will be evaluated by means of a set of endpoints addressing different facets of MS. There is no primary endpoint defined in the main study. These effectiveness endpoints include time to onset of confirmed CDP sustained for at least 24 and 48 weeks, change from baseline in EDSS score over time, relapse rates, MRI-based measures of disease activity and progression or degeneration, measures of cognition and PROs.

For a full list of effectiveness endpoints refer to Section 2.

After the Week 192 visit of the last enrolled patient, approximately 24 weeks and 48 weeks may be needed to allow the confirmation of the last event of the 24-week and 48 week-CDP (CDP/CDI confirmation visit). The main study analysis will be performed after the last CDP and CDI confirmation visit. With respect to CDP confirmation visits, only EDSS data at all the visits occurring in the treatment period of the study and LTE study (for patients who roll over to study MN39158) will be used. Appropriate statistical methods to account for missing confirmation visits will be defined in the SAP.

The evaluation of the clinical effectiveness of ocrelizumab will be based upon the events and assessments in-between baseline and week 192.

For patients who do not have an event by week 192, the time-to-event endpoints will be censored at the time of last visit in the study. A descriptive analysis based on the Kaplan-Meier method will be performed for the time to CDP and other time-to-event endpoints, such as the time to first relapse or the time to first event of disease activity. Cox proportional hazards regression will be used to identify predictors for CDP and other time-to-event endpoints. Variables to be included in the regression model will be region, gender, baseline EDSS, and some other variables, as appropriate. Further details will be specified in the SAP.

The change from baseline in EDSS, as well as other continuous variables, will be primarily analyzed using descriptive statistics, the mean, corresponding 95% CI, standard deviation and other statistics will be presented. Furthermore, the change of EDSS from baseline to each visit will be analyzed by linear mixed models for repeated measures (MMRM) adjusting for covariates such as the respective baseline score, geographical region, and baseline EDSS.

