Ocrelizumab—F. Hoffmann-La Roche Ltd 87/Protocol MA30143, Version 10.0 MRI activity will be evaluated from week 8 (baseline for MRI-based endpoints) to week 192.

For binary endpoints, e.g., NEP, NEDA and NEPAD, the proportion of patients meeting the endpoint at Week 96, 144 and 192 will be calculated and the corresponding twosided Clopper-Pearson 95% CI will be presented. Logistic regression models will be used to identify prognostic factors.

The annualized relapse rates will be analyzed using a Poisson regression model, adjusting for region and baseline EDSS. The total number of T1 Gd-enhanced lesions will be calculated as the sum of the individual number of T1 Gd-enhanced lesions at Weeks 24, 48, 96, 144 and 192. A Poisson model will be used to estimate the rate of lesion occurrence. A quasi Poisson or negative binomial regression may be applied as a sensitivity analysis.

An analysis of individual components of the composite endpoint will also be performed.

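### Plain Poisson is the main model for the relapse rate and the T1 Gd lesion rate; if the counts are overdispersed, the 95% CIs will be too narrow

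*Protocol*

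**What the plan says.** Protocol Section 6.4.1 sets the model for relapses: "The annualized relapse rates will be analyzed using a Poisson regression model, adjusting for region and baseline EDSS". For lesions, each patient's total is "calculated as the sum of the individual number of T1 Gd-enhanced lesions at Weeks 24, 48, 96, 144 and 192", and then "A Poisson model will be used to estimate the rate of lesion occurrence". The next sentence is the only provision for overdispersion: "A quasi Poisson or negative binomial regression may be applied as a sensitivity analysis". There is no check for overdispersion, no rule for changing model, and no scaled or robust standard error. Because that sentence follows the lesion model directly, it may cover lesions only; on that reading relapses have no stated alternative at all.

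On reporting, Section 6 says: "Corresponding 95% CIs will be presented as appropriate". On status, Section 6.4.1 says: "There is no primary endpoint defined in the main study". Section 6 leaves full statistical detail to a main-study SAP, which was not among the documents. The SAP supplied covers only the shorter infusion substudy and, in its Section 4.4, plans no efficacy analysis.

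**The concern.** A Poisson model takes the variance of a patient's count to equal its mean. If patients differ in underlying activity beyond what the covariates explain, the variance exceeds the mean. The rate estimate is then still sound, but its standard error is too small.

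Several features of the protocol make this plausible:

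- Lesion counts are summed within a patient over five scans, so lasting differences between patients accumulate.
- Patients can enter through either a relapse or MRI activity in the previous 12 months (Section 4.1.1), so baseline activity is mixed.
- Relapses in the past year and baseline MRI are summarized (Section 6.3), but neither is named as a covariate in these models.
- Patients with an unplanned pregnancy interrupt treatment but stay in the study (Sections 3.1.3 and 4.7.1), so on-drug and off-drug time are mixed.

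In a single-arm descriptive study, estimates with intervals are the main statistical output. Section 3.3 argues that "no direct comparators are required for this study" because the effect of existing treatments is established in the literature. Readers may therefore set these rates and intervals beside published figures, and an interval that is too narrow would mislead them there.

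**Working it through.** **Inputs from the documents.** The illustration uses 1,100 patients (Section 6.1), 192 weeks of treatment (Section 3.1) and five scans per patient (Section 6.4.1). Section 6.1 expects 15% of patients to have a disability progression event and "approximately the same number of patients to be prematurely withdrawn and censored before week 192".

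**Inputs that must be assumed.** The documents give no absolute relapse rate, lesion mean or dispersion; Section 1.2 reports relative reductions only. So there is no planned figure for these endpoints to reproduce, and everything below is a range.

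**Formulas.** Let φ be variance divided by mean. For gamma-Poisson (negative binomial) counts with shape k, φ = 1 + mean/k, so a smaller k means stronger clustering. The Poisson standard error is too small by a factor √φ. True coverage of its nominal 95% interval on the log scale is 2Φ(1.96/√φ) − 1.

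**Lesions, mean 0.2 per patient, n = 1,100.** Expected total 1,100 × 0.2 = 220. Poisson standard error of the log rate = 1/√220 = 0.0674. Poisson interval = 0.2 × exp(±1.96 × 0.0674) = 0.175 to 0.228. The correct interval multiplies the standard error by √φ.

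| φ | k implied at mean 0.2 | √φ | True coverage of Poisson CI | Correct 95% CI |
|---|---|---|---|---|
| 1 | no clustering | 1.00 | 95.0% | 0.175 to 0.228 |
| 1.2 | 1 | 1.10 | 92.6% | 0.173 to 0.231 |
| 2 | 0.2 | 1.41 | 83.4% | 0.166 to 0.241 |
| 3 | 0.1 | 1.73 | 74.2% | 0.159 to 0.251 |

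**Lesions, mean 0.05 per patient.** Coverage is 94.4% at k = 1, 93.0% at k = 0.3 and 89.0% at k = 0.1. With so few lesions the effect is small unless clustering is strong.

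**Relapses.** Assume an annualized rate of 0.05 to 0.15. Over 192/52.18 = 3.68 years this is 0.18 to 0.55 relapses per patient.

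| Annualized rate | k = 2: φ, coverage | k = 1: φ, coverage |
|---|---|---|
| 0.05 | 1.09, 93.9% | 1.18, 92.8% |
| 0.15 | 1.28, 91.7% | 1.55, 88.4% |

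**Simulation of the proposed alternatives.** Setting: 1,100 patients, 4,000 replicates, mean 0.2 lesions, five scans, 15% dropout spread evenly over 192 weeks, number of scans as offset.

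| φ | Poisson | Quasi-Poisson | Robust SE | CI width, robust/Poisson |
|---|---|---|---|---|
| 1 | 95.2% | 95.3% | 95.2% | 1.00 |
| 1.2 | 92.7% | 95.0% | 95.1% | 1.09 |
| 2 | 84.2% | 94.5% | 94.6% | 1.40 |
| 3 | 74.3% | 94.5% | 94.7% | 1.70 |

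A separate simulation with equal follow-up and wider assumed ranges agrees. For relapse rates of 0.05 to 0.20 with overdispersion (φ 1.09 to 2.47), Poisson coverage ran from 94.2% down to 78.4%. For lesion means of 0.05 to 0.5 with very strong clustering (φ 1.25 to 11), it ran from 91.3% down to 43.9%. Quasi-Poisson stayed between 94.0% and 95.8% in every scenario, including those with no overdispersion.

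**Side check on the lesion denominator.** The protocol does not say that missing scans count as zero. Only if they did, with no offset, would 15% withdrawal spread evenly lower the mean lesion total, by 0.15 × (24 + 48 + 96 + 144 + 192)/(5 × 192) = 0.15 × 0.525 = 7.9%. This does not apply to relapses.

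**The case against.** The strongest reply is that the protocol already anticipates the problem. It names both remedies, so what remains is which model is called main. In a study without hypotheses, a primary endpoint or multiplicity control, that ordering could be seen as preference. In addition, Section 6.4.1 names a Poisson model without naming a variance estimator, and the unseen main-study SAP could specify scaled or robust standard errors. The dispersion values are assumed: at a mean of 0.2, the 83% and 74% figures need k = 0.2 and k = 0.1, which is strong clustering. The calculations omit the planned adjustment of relapses for region and baseline EDSS, which would absorb some heterogeneity. The protocol plans no formal comparison of these rates with external figures.

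Part of this stands. The size is unknown, is modest for relapses under mild assumptions, and may be nil. The use beside published results is an inference from Section 3.3. The point about the variance estimator is weaker. Quasi-Poisson is Poisson with a scaled standard error, and the protocol lists it separately as an optional sensitivity analysis, so the natural reading is that the main model's standard error is unscaled. The ordering also matters more than preference: leaving the alternative optional allows the choice of reported interval to be made after the data are seen.

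**Conclusion.** The concern holds. As written, the main intervals for both count endpoints depend on variance equalling the mean, and the only relief is optional and secondary. If φ is 1 nothing is lost. At φ of 1.2 the understatement is slight (93% coverage); at 2 or 3 it is material (83% and 74%). On the assumed ranges, relapses lie mostly between 88% and 94%, and lesions could fall further if clustering is strong. These figures rest on assumed means and dispersion and on unscaled Poisson standard errors in the main analysis. The consequence is overstated precision for two of several descriptive measures; no confirmatory conclusion is affected. It is an improvement that should be made, held with medium confidence because the documents give no dispersion.

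**What to change.** For both endpoints, make negative binomial regression, or Poisson regression with quasi-likelihood or robust standard errors, the main analysis, and keep plain Poisson as the sensitivity analysis. In the same edit state the denominators: log follow-up time as offset for relapses, and log number of evaluable post-Week-8 scans as offset for lesions. The offsets are a clarification, since a rate already implies a denominator and the main-study SAP may state it.

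The change is one sentence and a model option. It can be made in the main-study SAP, which Section 6 says will be finalized before database lock; if that SAP already does this, the protocol wording only needs to be aligned. The price is wider intervals if the counts are overdispersed, by about 1.1, 1.4 or 1.7 times at φ of 1.2, 2 or 3, and essentially no change if they are not. Quasi-likelihood and robust standard errors leave the Poisson point estimate unchanged.

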6.4.2 Exploratory Endpoints

The exploratory effectiveness objective for the main study is to further assess the effectiveness of ocrelizumab 600 mg IV given every 24 weeks by monitoring endpoints as listed in Section 2.

The exploratory endpoints will be summarized descriptively and using methods similar to those used for the other effectiveness endpoints. Full details of the derivations and analyses of exploratory endpoints will be provided in the SAP.

6.5 SAFETY ANALYSES

6.5.1 Safety Outcome Measures

The safety outcome measures comprise the following: the incidence and nature of all adverse events, including findings on vital sign measurements, physical and neurological examinations, clinical laboratory tests, locally reviewed MRI for safety (non-MS CNS pathology), and concomitant medications.

6.5.2 Safety Analyses

The safety analysis will be performed on Safety population. Safety will be assessed through summaries of adverse events (including rates/incidence rates and corresponding 95% CIs) and clinical laboratory abnormalities.

All adverse events occurring on or after treatment on Day 1will be summarized by mapped term, appropriate thesaurus level and toxicity grade, and tabulated by body system and Preferred Term for individual adverse events within each body system. Grade 3 to 5 adverse events, serious adverse events, adverse events leading to treatment discontinuation, time to withdrawal from the study due to an adverse event, first adverse event leading to infusion adjustment, and time to first selected treatment-

Ocrelizumab—F. Hoffmann-La Roche Ltd 88/Protocol MA30143, Version 10.0 related adverse event will be summarized. In addition, all serious adverse events and deaths will be listed.

Associated laboratory parameters, such as hepatic function, renal function, and hematology values, will be grouped and presented together.

Ocrelizumab exposure will be summarized, including duration and dosage.

Concomitant medications recorded during the study will be summarized by frequency tables.

6.6 OTHER ANALYSIS

Other information, including, but not limited to, ADA, JCV, and biomarker endpoints will be analyzed. *Exploratory immunology analyses of SARS-CoV-2 antibody titers and SARS-CoV-2 T cell responses will be analyzed* as appropriate and details will be specified in a separate Biomarker Analysis Plan.

6.7 SUBGROUP ANALYSIS

Some effectiveness analyses may be undertaken in specific patient subgroups, for example, female patients interrupting treatment due to pregnancy. Details of these subgroup analyses will be presented in the SAP.

6.8 HANDLING OF MISSING DATA

Patients not completing the study for reasons different from lack of effectiveness or death will be defined as not reaching the NEDA endpoint ("NEDA=no"). The same rule will be used for NEP and NEPAD. More details about the missing data handling will be specified in statistical analysis plan.

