2. OBJECTIVES AND ENDPOINTS

The main study will evaluate the effectiveness and safety of ocrelizumab in patients who are in early stage of RRMS.

Specific objectives and corresponding endpoints for the study are outlined below.

Objectives	Corresponding Endpoints
Primary Objective:	
 To evaluate the effectiveness of ocrelizumab in early stage of RRMS 	 Evaluate clinical measures related to disease progression over 4 years in patients in the early stage of their RRMS disease
Overview of the effectiveness measures:	
 Different effectiveness measures 	Related to disability progression:
evaluated for ocrelizumab in early stage of RRMS	 Time to onset of CDP sustained for at least 24 weeks and 48 weeks

Table 1 Objectives and Corresponding Endpoints

Objectives	Corresponding Endpoints
	 Proportion of patients who have confirmed disability improvement (CDI), CDP for at least 24 weeks and 48 weeks at year 1, 2 and 4
	 Proportion of patients who have improved, stable or worsened disability compared with baseline measured by EDSS annually
	 Mean change from baseline in EDSS score over the course of the study
	Other clinical measures and composite endpoints:
	 Time to first protocol-defined event of disease activity
	Time to first relapse
	 Annualized relapse rate
	 Proportion of patient relapse free by week 48, 96, 144 and 192
	 Proportion of patients with no evidence of protocol- defined disease activity (NEDA) over week 96, week 144 and week 192 where disease activity is defined as at least one the following events: protocol-defined relapse; CDP based on increases in EDSS; a T1 Gd- enhanced lesion after Week 8; or a new and/or enlarging T2 hyperintense lesion on MRI after Week 8 compared to the Week 8 MRI scan.
	 Proportion of patients with no evidence of progression (NEP) defined as no progression sustained for at least 24 weeks on all of the following three components (CDP; 20% increase in timed 25 Foot Walk Test [T25FWT]; 20% increase in timed 9 hole peg test [9HPT]) between baseline and week 96/192
	 Proportion of patients with no evidence of progression sustained for at least 24 weeks and no active disease (NEPAD) defined as no progression on all of the three components of NEP (CDP, T25FWT, 9HPT), no new relapse and no enlarging or new T2 or T1 Gd- enhancing lesion between baseline and week 96/192

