T and B cells impact sub-study in France 288 weeks longitudinal, multi- center, sub-study (n=~50) Participating centers are restricted to French investigator centers with PBMC (peripheral blood mononuclear cell) technical and storage capacity.	 Impact of ocrelizumab-dependent B cell depletion on T cell subsets and functions in naïve RRMS patients, indirect impact of ocrelizumab on B cell repopulation and relationship between immunological biomarkers levels and clinical and/or subclinical change assessed by neurological markers in naïve RRMS patients treated with ocrelizumab
Immune sub-study in Germany and other selected countries (n=~80)	 Frequencies of circulating immune cell subsets (B cells, T cells, NK cells, antigen presenting cells)

Objectives	Corresponding Endpoints
Ocrelizumab shorter infusion substudy (approximately 700 patients: of which approximately 550 additional patients and approximately 150 currently participating in the main study)	 Proportion of patients with IRRs occurring during or within 24 hours following the first infusion after randomization to the shorter infusion substudy

The definition of a protocol-defined event of disease activity is the occurrence of at least one of the following while on treatment with ocrelizumab:

- a protocol-defined relapse as defined in Section 4.5.5
- CDP based on increases in EDSS (see Section 4.5.6)
- a T1 Gd-enhanced lesion after Week 8
- a new and/or enlarging T2 hyperintense lesion on MRI after Week 8 compared to the Week 8 MRI scan

3. STUDY DESIGN

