3.2 END OF STUDY AND LENGTH OF STUDY

The end of the main study is defined as the last patient last visit *in the Safety Follow-up period or last patient Week 192 visit, whichever occurs later.*

The end of the study treatment period has been defined as the date on which the last patient receiving the full study treatment reached the 192-week visit. *After the end of treatment period visit of the last enrolled patient, approximately 24 weeks and 48 weeks may be needed to allow the confirmation of the last event of the 24-week and 48-week CDP (CDP/CDI confirmation visit).* For those patients presenting with an EDSS change at the end of the treatment period and who roll over to the LTE study LIBERTO (Study MN39158), the 24-week and 48-week CDP confirmation visits will occur during the LTE study (Study MN39158). For patients who discontinue the study (e.g., move onto commercial ocrelizumab, or start treatment with another DMT), the EDSS CDP confirmatory assessments will not be performed.

The total length of the main study, from screening of the first patient to the end of the study depends on the recruitment rate and is expected to be approximately 356 weeks (~7 years). This includes an enrolment period of 116 weeks.

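### The NEDA/NEP/NEPAD missing-data rule leaves event-free patients who exit for lack of effectiveness or die without a score, and it is triggered by study completion rather than by reporting week (minor)

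*Protocol*

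**What the plan says.** Protocol 6.8 gives one rule for patients who leave: "Patients not completing the study for reasons different from lack of effectiveness or death will be defined as not reaching the NEDA endpoint". It continues "The same rule will be used for NEP and NEPAD" and closes with "More details about the missing data handling will be specified in statistical analysis plan".

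The endpoints are defined by window. Table 1 in Section 2 has "disease activity (NEDA) over week 96, week 144 and week 192", and takes NEP and NEPAD from baseline to Week 96/192. Section 6.4.1 says that for these binary endpoints "the proportion of patients meeting the endpoint at Week 96, 144 and 192 will be calculated", with Clopper-Pearson 95% intervals.

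Section 2 lists what counts as disease activity: "a protocol-defined relapse as defined in Section 4.5.5", CDP on EDSS, a T1 Gd-enhanced lesion after Week 8, and a new or enlarging T2 lesion after Week 8. Neither withdrawal nor death is on the list. Section 6 keeps early withdrawals in the ITT population whatever their reason, so each of them needs a value.

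The supplied SAP covers only the shorter infusion substudy (SAP Section 1) and plans no efficacy analysis (SAP 4.4). It therefore neither completes nor confirms the rule.

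**The concern.** There are two gaps.

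- **A group without a score.** The rule names the leavers it fails by excluding two exit reasons, and says nothing further about those two. A patient with no recorded event who leaves for lack of effectiveness, or dies, stays in the denominator with no assigned outcome. The programmer could score that patient as a success, as a failure, or drop the patient.
- **The trigger does not match the reporting weeks.** Not completing the study is a single whole-study status, while each endpoint belongs to a window. Section 3.2 writes "For patients who discontinue the study (e.g., move onto commercial ocrelizumab, or start treatment with another DMT", so a move to commercial drug counts as leaving. Followed literally, such a move at Week 150 turns a fully observed, event-free Week 96 record into a Week 96 failure. The same record followed by an exit at Week 150 for lack of effectiveness is not failed by the rule.

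At stake is how the NEDA, NEP and NEPAD proportions are read. No hypothesis test or power figure depends on them.

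**Working it through.** **Step 1: what the rule assigns.** The documents state no NEDA, NEP or NEPAD figure, so there is none to reproduce. Setting 6.8 beside the definitions in Section 2:

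| Record | Exit reason | Value from the text |
|---|---|---|
| Event before exit | any | no, by definition |
| No event | other reason | no, by 6.8 |
| No event | lack of effectiveness or death | none assigned |
| Event-free to Week 96, leaves later | other reason | literal reading: no at Week 96; window-specific reading: judged on data |

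**Step 2: inputs.**
- From Protocol 6.1: 1,100 patients; 15% with a CDP event and about the same number withdrawn before Week 192. So W = 0.15, or 165 patients.
- Assumed, not in the documents: share f leaving for lack of effectiveness or death, 5% to 40%; share e of those without a recorded event, one half; share q of later leavers event-free at the reporting week, 50% to 80%; withdrawals evenly spread over 192 weeks.

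**Step 3: the unscored group at Week 192.** u = W × f × e.
- Low: 0.15 × 0.05 × 0.5 = 0.00375, about 4 of 1,100.
- High: 0.15 × 0.40 × 0.5 = 0.030, or 33 of 1,100.

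Compared with scoring them as failures:
- Scored as successes, the proportion rises by u: 0.4 to 3.0 points.
- Dropped from the denominator, it rises by b/(1 − u) − b, where b is the proportion with these patients scored as failures. With b = 0.55: 0.55/0.99625 − 0.55 = 0.0021 to 0.55/0.97 − 0.55 = 0.0170, so 0.2 to 1.7 points. With b = 0.80: 0.3 to 2.5 points.

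u is proportional to both f and e, so other assumptions scale it directly.

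**Step 4: the completion trigger, literal reading.** Fall at week L = W × (1 − L/192) × (1 − f) × q.
- Week 96: 0.15 × 0.5 = 0.075. Then 0.075 × 0.60 × 0.50 = 0.0225 and 0.075 × 0.95 × 0.80 = 0.057, a fall of about 2 to 6 points.
- Week 144: 0.15 × 0.25 = 0.0375. Then 0.0375 × 0.30 = 0.011 and 0.0375 × 0.76 = 0.0285, a fall of about 1 to 3 points.
- With a constant withdrawal hazard instead of even timing, the share leaving after Week 96 is 0.15 − (1 − 0.85^0.5) = 0.072, giving 2.2 to 5.5 points. Week 144 becomes 1.1 to 2.7 points.
- On the window-specific reading the fall is zero at both weeks.

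**Step 5: scale.** Clopper-Pearson 95% half-widths at n = 1,100 are 3.0, 2.9 and 2.4 points for true proportions of 50%, 65% and 80%.

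**The case against.** The strongest reply is that 6.8 is a summary. It defers detail to an SAP, and Section 6 promises full statistical detail there before database lock. That SAP was not available and may already close both gaps. This stands as a limit on the conclusion. It does not remove the point, because 6.8 is not silent: it states a working rule, and an SAP built on the same words could inherit both gaps.

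The second reply is that the window-specific reading is the more natural one. The section concerns missing data, and a patient assessed through Week 96 has nothing missing for Week 96. This is fair, and it is why the effect of the trigger starts at zero. The text still does not say so.

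The third reply is that few patients fall in the unscored group. The early-discontinuation visit in Appendix 1 includes MRI, EDSS, MSFC and relapse recording, so many true failures will have a recorded event. Deaths should also be rare: Section 1.2 reports one in the ocrelizumab group of the two pooled RMS phase III studies over 96 weeks. This stands too, and makes the lower end of Step 3 more likely.

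Finally, other planned analyses limit the damage. Section 6.4.1 plans Kaplan-Meier analyses for endpoints "such as the time to first relapse or the time to first event of disease activity" and for time to CDP, plus an analysis of the composite's components. The first gives NEDA an estimate that does not use this rule. The others are partial checks for NEP and NEPAD.

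**Conclusion.** Minor. Both gaps are in the wording of 6.8: no value for event-free patients who leave for lack of effectiveness or die, and a trigger that does not match the reporting weeks. With 15% withdrawal and the assumed shares, the first moves Week 192 by about 0.2 to 3 points. The second lowers Week 96 by 0 to about 2 to 6 points, depending on the reading. Only the withdrawal rate and sample size come from the protocol. The study has no primary endpoint and its analyses are descriptive, so no test is affected.

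Three stronger conclusions that a reader might draw are not supported:
- *That the plan spares its treatment failures or counts them as successes.* Those with a recorded event already score no. The rest are unassigned, and the intent may well be that they fail too.
- *That the Week 96 proportion will be understated by several points.* That needs the literal reading, and the main-study SAP to keep it.
- *That NEP and NEPAD have no check at all.* The component analyses and the CDP and relapse Kaplan-Meier analyses are partial checks, although no Kaplan-Meier analysis is stated for T25FWT or 9HPT.

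**What to change.** Reword 6.8 and carry the text into the main-study SAP:

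> For each reporting week, a patient without a recorded event who leaves before that week for any reason, including lack of effectiveness or death, is scored NEDA/NEP/NEPAD = no. A patient assessed through that week is scored on events with onset up to it, with later visits used only to confirm progression that began before it.

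This keeps the plan's approach of counting non-completers as failures and extends it to the two unscored exit reasons. Initial EDSS worsening whose confirmation visit is missing should follow the method that Section 6.4.1 already leaves to the SAP. A missed MRI in a patient who stays in the study is a separate case that the SAP should also state.

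Keep the Clopper-Pearson analysis. Name the planned Kaplan-Meier analysis of time to first disease activity, read at each reporting week, as the NEDA sensitivity check. Cite the planned component, CDP and relapse analyses as partial checks for NEP and NEPAD. A censored analysis of those two composites is optional.

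The cost is two sentences in the protocol, the matching SAP text, and no new data.
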